7.2.2.2 Vital signs

Vital signs (body temperature, pulse rate, blood pressure) will be monitored at screening, EOT, and before administration of ceritinib at Day 1 of each cycle. Screening vital sign assessments performed within 4 days of first dosing do not need to be repeated at Cycle 1 Day 1. Vital signs will be measured according to normal medical practice.

7.2.2.3 Height and weight

Height and body weight will be measured. Weight will be measured at the screening visit, at Day 1 of each cycle, and at EOT. Screening weight assessment performed within 4 days of first dosing does not need to be repeated at Cycle 1 Day 1. Height will be collected at screening only.

7.2.2.4 Eastern Cooperative Oncology Group (ECOG) Performance status

The performance status will be assessed according to the ECOG performance status scale ([Oken 1982](#)). ECOG performance status will be assessed at screening, at Day 1 of each cycle and at the EOT visit ([Appendix M](#)). ECOG performance assessment performed within 4 days of first dosing does not need to be repeated at Cycle 1 Day 1.

7.2.2.5 Laboratory evaluations

Clinical laboratory analyses (hematology, biochemistry, coagulation, lipase, urinalysis, pregnancy test) are to be performed by the local laboratory according to the Visit Schedule outlined in [Table 7-1](#). Visit windows of \pm 4 days are allowed (except at cycle 1 Day 1). As

specified in Table 7-1, screening laboratory assessments performed within 4 days of first dosing do not need to be repeated at Cycle 1 Day 1.

Novartis must be provided with a copy of the local laboratory's certification (if applicable), and a tabulation of the normal ranges and units of each parameter collected in the eCRF. Any changes regarding normal ranges and units for laboratory values assessed during the study must be reported via an updated tabulation indicating the date of revalidation. Additionally, if at any time a patient has laboratory parameters obtained from a different (outside) laboratory, Novartis must be provided with a copy of the certification and a tabulation of the normal ranges and units for this laboratory as well. The investigator is responsible for reviewing all laboratory reports for patients in the study and evaluating any abnormalities for clinical significance.

More frequent laboratory examinations may be performed at the investigator's discretion if clinically indicated.

At any time during the study, abnormal laboratory parameters which are clinically relevant and require an action to be taken with study treatment (*e.g.*, require dose modification and/or interruption of study treatment, lead to clinical symptoms or signs, or require therapeutic intervention), whether specifically requested in the protocol or not, will be recorded on the Adverse Events eCRF page. Laboratory data will be summarized using the Common Terminology Criteria for Adverse events (CTCAE) version 4.0.3. Additional analyses are left to the discretion of the investigator.

7.2.2.5.1 Hematology

Hematology tests are to be performed by the local laboratory at screening, Day 1 and Day 15 of Cycles 1 and 2, at Day 1 of each subsequent cycle and at EOT according to the Visit Schedule outlined in [Table 7-1](#). The hematology panel includes hemoglobin, hematocrit, platelet count, total red blood cells (RBC), total white blood cells (WBC) count, and a WBC differential including neutrophils, lymphocytes, monocytes, eosinophils and basophils.

7.2.2.5.2 Biochemistry

Biochemistry tests are to be performed by the local laboratory at screening, Day 1 and Day 15 of Cycles 1 and 2, at Day 1 of each subsequent cycle and at EOT according to the Visit Schedule outlined in [Table 7-1](#). The full biochemistry panel includes creatine phosphokinase (CPK) (if total CPK is elevated \geq CTCAE Grade 2, then weekly measure isoenzymes in blood, and myoglobin in blood and urine until resolved to \leq CTCAE Grade 1), urea or blood urea nitrogen (BUN), creatinine, uric acid, sodium, magnesium, potassium, glucose, calcium, LDH, total protein, albumin, bicarbonate, phosphorus amylase, lipase, total cholesterol, high density lipoprotein (HDL), low density lipoprotein (LDL), and triglycerides. Additionally liver function test including AST/SGOT, ALT/SGPT, GGT, alkaline phosphatase, total, direct and indirect bilirubin will be measured.

7.2.2.5.3 Thyroid function

Thyroid function tests parameters include: thyroid stimulating hormone (TSH), free T3, and free T4.

Thyroid function should be assessed at screening, Day 1 of Cycle 1, Day 1 of Cycle 3, every 3 cycles from C3D1 during the treatment phase (or if clinically indicated), and at EOT.

7.2.2.5.4 Coagulation

International normalized ratio (INR) and pro-thrombin time (PT), activated partial thromboplastin time and fibrinogen will be measured at screening, Day 1 of Cycle 1, and during the treatment phase if clinically indicated.

7.2.2.5.5 Urinalysis

Urinalysis includes dipstick analysis of pH, bilirubin, ketones, leukocytes, protein, glucose, blood, and specific gravity, and will be performed at screening, Day 1 of each cycle and at EOT.

If clinically indicated based on macroscopic urinalysis results, a microscopic evaluation examination will be performed and will include Red Blood Cells, White Blood Cells, Casts, Crystals, Bacteria, and Epithelial cells.

If screening urinalysis results are $\geq +1$ for protein on dipstick reading, then total urinary protein must be ≤ 500 mg and measured creatinine clearance must be ≥ 50 mL/min/1.73m² in order for the patient to be eligible to participate in the study.

7.2.2.5.6 Pregnancy and assessments of fertility

Women of childbearing potential must undergo a serum pregnancy test at screening to confirm eligibility in the trial (≤ 4 days before first dose of study drug), and at EOT. Women of child-bearing potential must additionally undergo a monthly urine pregnancy test during the treatment phase.

In case of pregnancy, the patient must permanently stop study treatment immediately, withdraw from the trial, and the pregnancy must be reported on the Clinical Trial Pregnancy Form.

7.2.2.6 Radiological examinations (for safety)

Not applicable.

7.2.2.7 Cardiac assessments

7.2.2.7.1 Electrocardiogram (ECG)

A standard 12-lead ECG will be performed at screening, Day 1 of Cycles 1 and 2, at Day 1 of every other cycle and at EOT according to the Visit Schedule outlined in [Table 7-1](#).

The interpretation of the tracing must be made by a qualified physician and documented in the ECG section of the eCRF. Each ECG tracing should be labeled with the study number, patient initials (if permitted by local regulations), Patient Number, date, and kept in the source documents at the study site. Only clinically significant abnormalities should be reported in the Adverse Events eCRF. Clinically significant abnormalities present when the patient signed informed consent should be reported on the Medical History eCRF page. Clinically significant

findings must be discussed with the Novartis Medical Monitor prior to enrolling the patient in the study. New or worsened clinically significant findings occurring after informed consent must be recorded on the Adverse Events eCRF page.

7.2.2.7.2 Cardiac imaging - MUGA (multiple gated acquisition) scan or echocardiogram

MUGA (multiple gated acquisitions) scan or echocardiogram (ECHO) will be used to assess LVEF at screening and during the treatment phase as clinically indicated to assess signs or symptoms of cardiotoxicity. In case of clinically significant abnormalities, they should be reported on the Adverse Events eCRF.

[figure not shown]
In case a patient develops left ventricular systolic dysfunction while on study treatment dose adjustment guidelines described in [Section 6.3](#) must be followed.

[figure not shown]
7.2.2.7.3 Cardiac enzymes

[figure not shown]
Cardiac enzymes (Cardiac troponin-I or troponin-T) will be measured at screening and during the treatment phase if clinically indicated, especially in case of LVEF decrease.

7.2.3 Pharmacokinetics

Not Applicable.

7.2.5 Other assessments

No additional tests will be performed on patients entered into this study.

8 Safety monitoring and reporting

8.1 Adverse events

8.1.1 Definitions and reporting

An adverse event (AE) is defined as the appearance of (or worsening of any pre-existing) undesirable sign(s), symptom(s), or medical condition(s) that occur after patient's signed informed consent has been obtained.

For patients who sign the ICF, all AEs will be captured in the AE eCRF from time of signature through 30 days after permanent study treatment discontinuation. For patients who fail the screening, only SAEs will be captured in the AE eCRF page.

Abnormal laboratory values or test results occurring after informed consent constitute adverse events only if they induce clinical signs or symptoms, are considered clinically significant, require therapy (e.g., hematologic abnormality that requires transfusion or hematological stem cell support), or require changes in study medication(s).

Adverse events that begin or worsen after informed consent should be recorded in the Adverse Events eCRF. Conditions that were already present at the time of informed consent should be recorded in the Medical History eCRF. Adverse event monitoring should be continued for at least 30 days following the last dose of study treatment. Adverse events (including lab abnormalities that constitute AEs) should be described using a diagnosis whenever possible, rather than individual underlying signs and symptoms. When a clear diagnosis cannot be identified, each sign or symptom should be reported as a separate Adverse Event.

Adverse events will be assessed according to the Common Terminology Criteria for Adverse Events (CTCAE) version 4.03. If CTCAE grading does not exist for an adverse event, the severity of mild, moderate, severe, and life-threatening, corresponding to Grades 1-4, will be used. CTCAE Grade 5 (death) will not be used in this study; rather, information about deaths will be collected through a Death form.

The occurrence of adverse events should be sought by non-directive questioning of the patient (subject) during the screening process after signing informed consent and at each visit during the study. Adverse events also may be detected when they are volunteered by the patient (subject) during the screening process or between visits, or through physical examination, laboratory test, or other assessments. As far as possible, each adverse event should be evaluated to determine:

1. The severity grade (CTCAE Grade 1-4)
2. Its duration (Start and end dates)
3. Its relationship to the study treatment (Reasonable possibility that AE is related: No, Yes) or
Its relationship to the study treatment (Reasonable possibility that AE is related: No, Yes, investigational treatment, Yes, the study treatment (non-investigational), Yes, both and/or indistinguishable)
4. Action taken with respect to study or investigational treatment (none, dose adjusted, temporarily interrupted, permanently discontinued, unknown, not applicable)
5. Whether medication or therapy taken (no concomitant medication/non-drug therapy, concomitant medication/non-drug therapy)
6. Outcome (not recovered/not resolved, recovered/resolved, recovering/resolving, recovered/resolved with sequelae, fatal, unknown)
7. Whether it is serious, where a serious adverse event (SAE) is defined as in [Section 8.3](#)

All adverse events should be treated appropriately. If a concomitant medication or non-drug therapy is given, this action should be recorded on the Adverse Event eCRF.

Once an adverse event is detected, it should be followed until its resolution or until it is judged to be permanent, and assessment should be made at each visit (or more frequently, if necessary) of any changes in severity, the suspected relationship to the study treatment, the interventions required to treat it, and the outcome.

Progression of malignancy (including fatal outcomes), if documented by use of appropriate method (as per RECIST 1.1 criteria for solid tumors or as per Cheson's guidelines for hematological malignancies), should not be reported as a serious adverse event or adverse event.

Adverse events separate from the progression of malignancy (example, deep vein thrombosis at the time of progression or hemoptysis concurrent with finding of disease progression) will be reported as per usual guidelines used for such events with proper attribution regarding relatedness to the drug.

8.1.2 Laboratory test abnormalities

8.1.2.1 Definitions and reporting

Laboratory abnormalities will be assessed according to the Common Terminology Criteria for Adverse Events (CTCAE) version 4.03. Laboratory abnormalities that constitute an Adverse event in their own right (are considered clinically significant, induce clinical signs or symptoms, require concomitant therapy or require changes in study treatment), should be recorded on the Adverse Events eCRF. Whenever possible, a diagnosis, rather than a symptom should be provided (e.g. anemia instead of low hemoglobin). Laboratory abnormalities that meet the criteria for Adverse Events should be followed until they have returned to normal or an adequate explanation of the abnormality is found. When an abnormal laboratory or test result corresponds to a sign/symptom of an already reported adverse event, it is not necessary to separately record the lab/test result as an additional event.

Laboratory abnormalities, that do not meet the definition of an adverse event, should not be reported as adverse events. A Grade 3 or 4 event (severe) as per CTCAEv4.03 does not automatically indicate an SAE unless it meets the definition of serious as defined below and/or as per investigator's discretion. A dose hold or medication for the lab abnormality may be required by the protocol and is still, by definition, an adverse event.

8.2 Adverse events of special interest

Adverse events of special interest to be monitored for ceritinib have also been identified and include: hepatotoxicity, interstitial lung disease/pneumonitis, QT interval prolongation, bradycardia, hyperglycemia, gastrointestinal toxicity (nausea, vomiting and diarrhea), and pancreatitis (including lipase and amylase elevations). Details regarding these adverse events are provided in the [Investigator's Brochure] for ceritinib. Potential emergent new AEs will be monitored during the course of the study.

8.3 Serious adverse events

8.3.1 Definitions

Serious adverse event (SAE) is defined as one of the following:

- Is fatal or life-threatening
- Results in persistent or significant disability/incapacity
- Constitutes a congenital anomaly/birth defect

- Is medically significant, i.e., defined as an event that jeopardizes the patient or may require medical or surgical intervention to prevent one of the outcomes listed above
- Requires inpatient hospitalization or prolongation of existing hospitalization,
- Note that hospitalizations for the following reasons should not be reported as serious adverse events:
 - Routine treatment or monitoring of the studied indication, not associated with any deterioration in condition (specify what this includes)
 - Elective or pre-planned treatment for a pre-existing condition that is unrelated to the indication under study and has not worsened since signing the informed consent
 - Treatment on an emergency outpatient basis for an event not fulfilling any of the definitions of a SAE given above and not resulting in hospital admission
 - Social reasons and respite care in the absence of any deterioration in the patient's general condition
- Note that treatment on an emergency outpatient basis that does not result in hospital admission and involves an event not fulfilling any of the definitions of a SAE given above is not a serious adverse event

8.3.2 Reporting

To ensure patient safety, every SAE, **regardless of suspected causality**, occurring after the patient has provided informed consent and until at least 30 days after the patient has stopped study treatment must be reported to Novartis within 24 hours of learning of its occurrence.

SAE collection starts at time of ICF signature whether the patients is a screen failure or not.

Any SAEs experienced after this 30 days period should only be reported to Novartis if the investigator suspects a causal relationship to the study treatment. Recurrent episodes, complications, or progression of the initial SAE must be reported as follow-up to the original episode within 24 hours of the investigator receiving the follow-up information. An SAE occurring at a different time interval or otherwise considered completely unrelated to a previously reported one should be reported separately as a new event.

Information about all SAEs (either initial or follow up information) is collected and recorded on the Serious Adverse Event Report Form on a paper SAE Form. The investigator must assess and record the relationship of each SAE to each specific study treatment (if there is more than one study treatment), and complete the SAE Report Form in English.

The SAEs recorded on the paper SAE form should be faxed to [REDACTED] **within 24 hours of awareness of the SAE** to the local Novartis Drug Safety and Epidemiology Department (DS&E). The original copy of the SAE Report Form and the fax confirmation sheet must be kept with the case report form documentation at the study site.

Note that any follow up information provided should describe whether the event has resolved or continues, if and how it was treated, and whether the patient continued or withdrew from study participation. Each re-occurrence, complication, or progression of the original event should be reported as a follow-up to that event regardless of when it occurs.

The follow up information should describe whether the event has resolved or continues, if and how it was treated, and whether the patient continued or withdrew from study participation.

Refer to [Section 7.1.1.2](#) for additional details regarding the reporting of SAEs which occur during the screening period.

8.4 Emergency unblinding of treatment assignment

Not applicable.

8.5 Pregnancies

To ensure patient safety, each pregnancy occurring while the patient is on study treatment must be reported to Novartis within 24 hours of learning of its occurrence. The pregnancy should be followed up to determine outcome, including spontaneous or voluntary termination, details of the birth, and the presence or absence of any birth defects, congenital abnormalities, or maternal and/or newborn complications.

Pregnancy should be recorded on a Clinical Trial Pregnancy Form and reported by the investigator to the oncology Novartis DS&E department. Pregnancy follow-up should be recorded on the same form and should include an assessment of the possible relationship to the Novartis study treatment of any pregnancy outcome. Any SAE experienced during pregnancy must be reported on the SAE Report Form.

Pregnancy outcomes must be collected for the female partners of any males who took study treatment in this study. Consent to report information regarding these pregnancy outcomes should be obtained from the mother.

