 29. Cirrhosis of the liver or known hepatitis B or C infection that is either acute or is considered chronic because the virus did not become undetectable:
 - a. Hepatitis C Virus (HCV) infection: acute or chronic infection as depicted by a positive HCV RNA testing (note: in a patient with known anti-HCV but with a negative test for HCV RNA, re-testing for HCV RNA 4-6 months later is requested to confirm the resolution of HCV infection)
 - b. Hepatitis B Virus (HBV) infection: acute infection (HBsAg+ with or without HBeAg+ or detectable serum HBV DNA), HBV carriers as evidence by ongoing presence of HBsAg and detectable serum HBV DNA levels
 30. Patients who have received investigational agents within $\leq 5t_{1/2}$ of the agent (or ≤ 4 weeks when half-life is unknown) prior to starting study drug
 31. Known diagnosis of human immunodeficiency virus (HIV) infection (HIV testing is not mandatory)
 32. Patient has a history of non-compliance to medical regimen
 33. Pregnant or nursing (lactating) women, confirmed by a positive hCG laboratory test
 34. Women of child-bearing potential, defined as all women physiologically capable of becoming pregnant, **unless** they are using highly effective methods of contraception (defined below). Highly effective contraception must be used by both sexes (female patients and their male partners) during dosing and for 3 months after the last dose of study medication

Highly effective contraception methods include:

- Total abstinence (when this is in line with the preferred and usual lifestyle of the subject). Periodic abstinence (e.g., calendar, ovulation, symptothermal, post-ovulation methods) and withdrawal are not acceptable methods of contraception
- Female sterilization (have had surgical bilateral oophorectomy with or without hysterectomy) total hysterectomy, or tubal ligation at least six weeks before taking study treatment. In case of oophorectomy alone, only when the reproductive status of the woman has been confirmed by follow up hormone level assessment
- Male sterilization (at least 6 months prior to screening. The vasectomized male partner should be the sole partner for that subject.
- Use of oral, injected or implanted hormonal methods of contraception or placement of an intrauterine device (IUD) or intrauterine system (IUS), or other forms of hormonal contraception that have comparable efficacy (failure rate $<1\%$), for example hormone vaginal ring or transdermal hormone contraception.

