In case of use of oral contraception, women should have been stable on the same pill for a minimum of 3 months before taking study treatment.

Reliable double-barrier contraception method should be used and maintained throughout the study and for 3 months after study treatment discontinuation.

Women of child-bearing potential (sexually mature) who have not undergone a hysterectomy or who have not been naturally postmenopausal for at least 12 consecutive months (i.e., who has had menses any time in the preceding 12 consecutive months), must have a negative serum pregnancy test \leq 14 days prior to starting study drug.

Post-menopausal women are allowed to participate in this study. Women are considered post-menopausal and not of child bearing potential if they have had 12 months of natural (spontaneous) amenorrhea with an appropriate clinical profile (e.g. age appropriate, history of vasomotor symptoms) or six months of spontaneous amenorrhea with serum FSH levels > 40 mIU/mL or have had surgical bilateral oophorectomy (with or without hysterectomy) at least six weeks prior to entry in the study. In the case of oophorectomy alone, only when the reproductive status of the woman has been confirmed by follow up hormone level assessment, then she will be considered not of child bearing potential.

35. Fertile males not willing to use contraception. Fertile males must use condom with spermicide. Highly effective contraception, as defined above, must be used by both sexes (male patients and their female partners) during study treatment and for 3 months after the last dose of study medication and should not father a child in this period. A condom is required to be used also by vasectomized men in order to prevent delivery of the drug via seminal fluid.

6 Treatment

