Urine protein electrophoresis (UPEP) ⁷	D	7.2.1.3.2.	X	Every 8 weeks (±4 days) after first dose of study drug (Day 1 of every odd cycle)						X		
Free light chain ⁷	D	7.2.1.3.3.	X	Every 8 weeks (±4 days) after first dose of study drug (Day 1 of every odd cycle)						X		
Serum protein electrophoresis (SPEP) ⁷	D	7.2.1.3.4.	X	Every 8 weeks (±4 days) after first dose of study drug (Day 1 of every odd cycle)						X		
MRI/CT Scans (For plasmacytoma Only)	D	7.2.1.3.5.	X	Every 8 weeks (±4 days) after first dose of study drug (Day 1 of every odd cycle)								
Bone Marrow Biopsy or aspirate	D	7.2.1.3.6.	X	To confirm response of CR								
Chronic Lymphocytic Leukemia (CLL)												
Examination for enlarged spleen or liver	D	7.2.1.2.1	X	To confirm response of CR								

Visit Number	Category	Reference to assessment	Screening phase	Treatment Phase						Post treatment follow-up phase	Survival phase	
				Screening		C1	C2	Subsequent cycles		EOT		
			1	2	3	4	5	6		777	501	701
Cycle days ¹			-28 to -1		1	15	1	15	1		EOT + 30 (±4) days	EOT + every 3 months ²
Evaluation of transfusion dependency	D	7.2.1.4.5	X	X	X	X	X	X		X		

¹ A complete cycle is defined as 28 days.

² Additional survival assessments may be performed outside the 3 months follow-up schedules if a survival update is required for an interim assessment to meet safety or regulatory needs.

³ Tumor assessments at EOT are required for patients who discontinue study treatment before the first scheduled post-screening tumor assessment and for patients whose previous tumor assessment did not demonstrate PD and was done at least 8 weeks (± 4 days) prior to end of treatment visit.

⁴ These assessments should be performed only if the screening assessment occurred > 4 days from Cycle 1 Day 1. The patient must continue to meet all eligibility criteria on C1D1, as they did during the screening period prior to first dose.

⁵ Tumor assessments include CT/MRI of the chest abdomen and pelvis at all timepoints. Tumor assessments are described in [Section 7.2.1](#)

⁶ Women of childbearing potential must undergo a serum pregnancy test at screening and EOT. Women of child-bearing potential will undergo a monthly urine pregnancy tests during the study.

⁷ For patients who have a response of PR or greater, a confirmation assessment must be performed at least 4 weeks after the initial observation.

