11.3 Informed consent procedures

Eligible patients may only be included in the study after providing written (witnessed, where required by law or regulation), IRB/IEC/REB-approved informed consent. Informed consent must be obtained before conducting any study-specific procedures (i.e. all of the procedures described in the protocol). The process of obtaining informed consent should be documented in the patient source documents. The date when a subject's Informed Consent was actually obtained will be captured in their eCRFs.

Novartis will provide investigators in a separate document with a proposed informed consent form (ICF) that is considered appropriate for this study and complies with the ICH and GCP guideline and regulatory requirements. Any changes to this ICF suggested by the investigator must be agreed to by Novartis before submission to the IRB/IEC/REB, and a copy of the approved version must be provided to the Novartis monitor after IRB/IEC approval.

Women of child bearing potential and fertile males should be informed that taking the study medication may involve unknown risks to the fetus if pregnancy were to occur during the study and agree that in order to participate in the study they must adhere to the contraception requirement for the duration of the study. Women of child bearing potential must agree to adhere to contraception requirement until at least 3 months after the final dose of study treatment. Fertile males must agree to adhere to contraception requirement until at least 3 months after the final dose of study treatment. If there is any question that the patient will not reliably comply, they should not be entered in the study.

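### Section 8.5 makes a female patient's pregnancy reportable only if it occurs on study treatment, although contraception is required for 3 months after the last dose

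*Protocol*

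**What the plan says.** **Contraception.** Protocol 5.3 item 34 requires highly effective contraception "during dosing and for 3 months after the last dose of study medication". Protocol 11.3 repeats the period at consent: "Women of child bearing potential must agree to adhere to contraception requirement until at least 3 months after the final dose of study treatment". Item 35 of 5.3 sets the same 3 months for male patients, who "should not father a child in this period".

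**Reporting.** Protocol 8.5 states that "each pregnancy occurring while the patient is on study treatment must be reported to Novartis within 24 hours of learning of its occurrence", and that the pregnancy is then followed to its outcome. It names no period after treatment for patients. For partners it says: "Pregnancy outcomes must be collected for the female partners of any males who took study treatment in this study". That sentence has no time limit.

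**Testing.** A footnote to Protocol Table 7-1 says: "Women of childbearing potential must undergo a serum pregnancy test at screening and EOT". Protocol 7.2.2.5.6 adds: "Women of child-bearing potential must additionally undergo a monthly urine pregnancy test during the treatment phase". The end-of-treatment (EOT) visit is due within 7 days of stopping (7.1.3.1), and Table 7-1 marks no pregnancy test after it.

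**Other safety reporting.** Adverse events and serious adverse events (SAEs) are collected for at least 30 days after treatment (8.1.1, 8.3.2). Beyond that, "Any SAEs experienced after this 30 days period should only be reported to Novartis if the investigator suspects a causal relationship to the study treatment".

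**The concern.** The contraception rule marks out a period in which the protocol wants pregnancy avoided. Protocol 11.3 introduces the requirement by referring to unknown risks to the fetus. One would expect a pregnancy that happens in that period despite the precautions to be recorded and followed, since that is how such a risk comes to be known.

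Section 8.5 stops short of that. A site that follows it exactly has no duty to report a patient who conceives, for example, two weeks after her last dose, and no duty to follow the outcome. What is at stake is the completeness of the pregnancy data, not any efficacy result.

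**Working it through.** No sample size, power or error rate depends on this point, and the plan gives no figure to reproduce. The check sets the windows side by side, counted from the last dose, taking 3 months as about 90 days (assumption).

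- Contraception, female patients (5.3 item 34; 11.3): day 0 to about day 90.
- Required reporting of a patient's pregnancy conceived after the last dose (8.5): 0 of those 90 days.
- Scheduled testing (Table 7-1; 7.1.3.1; 7.2.2.5.6): ends at EOT, day 7 at the latest if treatment is stopped for good on the last dosing day. That leaves 90 − 7 = 83 days or more without a scheduled test.
- General AE and SAE collection (8.1.1; 8.3.2): at least to day 30. For a patient followed only for that minimum, the remaining 90 − 30 = 60 days are covered only for SAEs that the investigator suspects are related.
- Outcomes of pregnancies in partners of male patients (8.5): no limit.

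Next, does any other section close the gap for a female patient?

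1. Protocol 7.2.2.5.6 calls for the pregnancy form, but together with stopping treatment at once, so it also describes a pregnancy found on treatment.
2. Safety follow-up (7.1.4.1) covers adverse events and concomitant medications. Pregnancy is not mentioned.
3. Survival contacts (7.1.4.3) collect survival information only.
4. The SAE definition (8.3.1) lists a birth defect but not pregnancy. A complication or birth defect that meets the definition is reportable for at least 30 days whatever the cause, and later if suspected to be related (8.3.2). An uncomplicated pregnancy is not caught.
5. Protocol 8.5 also requires any SAE during pregnancy to go on the SAE form, with no causality condition. Whether this reaches pregnancies outside the section's opening sentence is unclear. Even if it does, it captures the event and not the pregnancy or its outcome.
6. The Table 7-1 footnote places the monthly urine tests during the study, whereas 7.2.2.5.6 places them in the treatment phase. The table's columns support the latter.

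None of these extends reporting or outcome follow-up to a patient who conceives after her last dose. There is also an asymmetry inside 8.5. Read literally, a pregnancy conceived on day 60 by the partner of a treated man has its outcome collected, while one conceived on day 60 by a treated woman does not.

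**The case against.** Several points on the other side are sound and limit the finding.

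- *Pregnancies begun on treatment.* The duty depends on when the pregnancy occurs, and the 24-hour clock starts when the site learns of it. A pregnancy that began on treatment but is discovered weeks later remains reportable. A reader might infer that all pregnancies in the 3 months are lost. The text does not support that: only conceptions after the last dose fall outside, and a site may still report them voluntarily.
- *Safety contact.* A reader might infer that two thirds of the window (60 of 90 days) has no safety contact. That is not true of every patient. The 30 days is a stated minimum, and patients whose treatment was interrupted or stopped for an adverse event are followed weekly for 4 weeks and then at about 4-week intervals until resolution or stabilization (6.3.4; 7.1.4.1).
- *Partners.* A reader might see the missing window for partner pregnancies as a second gap. It is the reverse: an open-ended duty is wider than 3 months, and adding a window would narrow it. What is absent is a procedure for detecting partner pregnancies after treatment.
- *Exposure.* The documents do not show that every conception in the window is an exposed one. Protocol 1.2.4.1.2 gives a single-dose half-life of 31 to 41 h and a fall in apparent clearance from 88.5 to 33.2 L/h at steady state, a ratio of 88.5 / 33.2 = 2.67. If half-life lengthens in proportion (assumption), it becomes 31 × 2.67 ≈ 83 h to 41 × 2.67 ≈ 109 h. Five half-lives at the upper value is 5 × 109 = 545 h, about 23 days, and 8 weeks is 1,344 / 109 ≈ 12 half-lives. Late conceptions may thus carry little exposure. On the same assumption, the fraction left 7 days (168 h) after the last dose is 0.5^(168/83) ≈ 25% to 0.5^(168/109) ≈ 34%, so early ones may well be exposed.

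None of this removes the mismatch for female patients. The protocol chose 3 months without giving its reason, and 8.5 does not follow that choice.

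**Conclusion.** The mismatch stands, for female patients only. A pregnancy conceived after the last dose, but within the 3 months for which contraception is required, need not be reported or followed to outcome, apart from complications or birth defects caught by the SAE rules.

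It is probably small in number. That is an assumption, resting on few women of child-bearing potential being expected in a population with refractory cancer. The primary analysis, sample size and error rates are untouched. Because 8.5 states a rule that under-collects when followed exactly, this is more than a missing detail, and it should be corrected. The finding takes the 3-month period as given and does not judge whether it is the right length.

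**What to change.** Reconcile Protocol 8.5 with 5.3 and 11.3: make a patient's pregnancy reportable, and followed to outcome, if it occurs on study treatment or in the 3 months after the last dose that those sections already state. Leave the sentence on partners of male patients unchanged.

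Optionally, ask about pregnancy at the first 3-monthly survival contact when that contact takes place. It can only be a supplement. It falls near the end of the window and could miss a very recent conception. The sponsor may also drop survival follow-up (7.1.4.3), and the SAP (section 2) records it as closed on August 4, 2016. The wording of 8.5 must therefore stand alone.

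The duty starts when the site learns of a pregnancy, so no visit or test is added. The cost is one sentence in 8.5 and a few more pregnancy forms, plus one question if the optional step is taken.
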